#### **6.4.3. Derivation of Health Outcome Endpoints**

##### AIM-D Related Endpoints Derivation

As described in SAP Section [5.3.4.8](#) (copied from protocol Section 6.3.1), the AIM-D was developed as a daily eDiary with a recall period 24 hours. By design, it is collected in the today diary only. The scoring of the following endpoints is completed in 2 steps.

- Monthly Performance of Daily Activities domain score of the AIM-D
- Monthly Physical Impairment domain score of the AIM-D
- Monthly Total Score of the AIM-D

#### Step 1: Calculate AIM-D daily domain score

Daily performance of daily activities score will be calculated based on the summation of items 1-5 and 10 and 11, ranging from 0-35. A daily performance of daily activities domain score will be calculated if 4 or more item scores have non-missing responses. When the response category "I did not have <errands, leisure or social, strenuous activities> planned" (items 2, 4, and 5), is selected, the response will be considered missing. The corresponding performance of daily activities domain score will be calculated by summing the non-missing item scores and dividing by the number of non-missing items and then multiplying by 7, provided that 4 or more item scores are available; otherwise it will be set to missing. The raw daily score will be transformed to a 0-100 scale by multiplying by 100 and dividing by the highest raw score (35).

Daily physical impairment scores will be calculated based on the summation of items 6-9, ranging from 0-20. A daily physical Impairment score will be calculated if 2 or more item scores have non-missing responses. The corresponding physical Impairment score will be calculated by summing the non-missing item scores and dividing by the number of non-missing items and then multiplying by 4, provided that 2 or more item scores are available; otherwise it will be set to missing. The raw daily score will be transformed to a 0-100 scale by multiplying by 100 and dividing by the highest raw score (20).

A daily total score will be calculated based on the summation of items 1-11, ranging from 0-55. A Total Score will be calculated if 6 or more items scores have non-missing responses. When the response category "I did not have <errands, leisure or social, strenuous activities> planned" (items 2, 4, and 5), is selected, the response will be considered missing. The corresponding Total Score will be calculated by summing the non-missing item scores and dividing by the number of non-missing items and then multiplying by 11, provided that 6 or more item scores are available; otherwise it will be set to missing. The raw score will be transformed to a 0-100 scale by multiplying by 100 and dividing by the highest raw score (55).

#### Step 2: Calculate Monthly Scores and Baseline Score

Monthly scores will be calculated using the average daily scores only if there are at least 14 non-missing daily scores in the corresponding monthly (28-day) period. The corresponding monthly

scores will be calculated by summing the non-missing daily domain scores and dividing by the number of non-missing daily domain, provided that 14 or more daily scores are available; otherwise it will be set to missing.

Monthly activity level score will be calculated by summing the non-missing daily scores and dividing by the number of these scores, provided that 14 or more daily scores are available in the corresponding monthly (28-day) period; otherwise it will be set to missing. Same rule will be applied to the calculation of monthly activity limitation score.

#### MSQ Related Endpoints Derivation

MSQ v2.1 consists of 14 items with a 4-week recall period. The scoring of the MSQ is completed in following 3 steps.

Step 1: Final item value assignment.

Precoded item values and final item values for each MSQ item response are shown in [Table 6-11](#).

**Table 6-11      Item Values for MSQ Item Responses**

Response Categories	Precoded Item Value	Final Item Value
None of the time	1	6
A little bit of the time	2	5
Some of the time	3	4
A good bit of the time	4	3
Most of the time	5	2
All of the time	6	1

Step 2: Computation of raw domain(dimension) scores

Once a final item value has been assigned to each item, a raw score can be computed for each MSQ domain. Role Function Restrictive domain includes Items 1 - 7, Role Function Preventive domain includes Items 8 - 11, and Emotional Function domain includes Items 12 - 14. The raw score for each domain is the algebraic sum of the final item values for all items in that domain.

Missing data handling: if a respondent answered at least half of the items in a domain (or half plus one in the case of scales with an odd number of items), a missing item value can be estimated using the average of the other completed items within the same dimension.

In detail, for MSQ v2.1 Role Function Restrictive domain, the 7 individual item responses using final item value will be summed, resulting in the raw domain score ranging from 7 to 42 with higher scores indicating better quality of life. If there are missing item responses, the raw domain score will be calculated by summing the non-missing item responses using final item value and dividing by the number of non-missing items and then multiplying by 7 provided that 4 or more items in the domain are completed; otherwise it will be set to missing. For MSQ v2.1 Role Function Preventive and Emotional domains, the raw domain scores will be calculated similarly using final item value respectively. If there are missing item responses, the corresponding raw domain score will be calculated by summing the non-missing item responses using final item value and dividing by the number of non-missing items and then multiplying by the number of questions in that domain provided that 2 or more domain items are completed; otherwise it will be set to missing.

Step 3: Linear transformation to a 0 to 100 scale.

The transformation formula for each MSQ 2.1 domain are listed below:

- Role Function -Restrictive: 
$$\frac{(raw\ score - 7) * 100}{35}$$
- Role Function-Preventive: 
$$\frac{(raw\ score - 4) * 100}{20}$$
- Emotional Function: 
$$\frac{(raw\ score - 3) * 100}{15}$$

#### HIT-6 Total Score Derivation

For HIT-6 total score, pre-coded item values and final item values for each item response are shown in [Table 6-12](#). Total score is calculated by summing 6 sub-item responses, resulting in the total score ranging from 36 to 78 with higher scores indicating greater impact. If any sub-item is missing, then total score will be missing.

**Table 6-12 Item Values for HIT-6 Item Response**

Response Categories	Precoded Item Value	Final Item Value
Never	0	6
Rarely	1	8
Sometimes	2	10
Very Often	3	11
Always	4	13

The HIT-6 instrument has a recall period of 4 weeks for 3 of the 6 items.

#### MIDAS Related Endpoints Derivation

MIDAS total score is derived as the sum of first 5 of questions (i.e., the sum of days missing work or school, Productivity at work or school reduced, Not do household work, Productivity in household work reduced, Miss family social or leisure activities). If any sub item is missing, the MIDAS total score will be missing.

The MIDAS absenteeism score is derived as the sum of Questions 1, 3 and 5. If any sub item is missing, then the MIDAS absenteeism score will be missing. The MIDAS presenteeism score is derived as the sum of Questions 2 and 4. If any sub item is missing, then the MIDAS presenteeism score will be missing.

#### WPAI:MIGRAINE Related Endpoints Derivation

WPAI outcomes are expressed as impairment percentages, with higher numbers indicating greater impairment and less productivity, i.e., worse outcomes, as follows:

Questions:

- Q1 currently employed (working for pay).
- Q2 missed work hours because of problems associated with your migraine
- Q3 missed work hours due to other reason.
- Q4 hours actually worked.
- Q5 migraine affected productivity while working.
- Q6 migraine affected regular daily activity.

Scores:

Multiply scores by 100 to express in percentages.

- Percent work time missed due to migraine (absenteeism):  $Q2/(Q2 + Q4)$
- Percent impairment while working due to migraine (presenteeism):  $Q5/10$
- Percent overall work impairment due to migraine (overall work productivity loss):  $Q2/(Q2 + Q4) + [(1 - (Q2/(Q2 + Q4))) \times (Q5/10)]$
- Percent activity impairment due to migraine (regular activity impairment):  $Q6/10$

If the response to Q1 ("Currently employed?") is *No* or missing, absenteeism, presenteeism, and overall work productivity loss will all be set to missing.

#### EQ-5D-5L

With the EQ-5D-5L, rating levels can be coded as numbers 1, 2, 3, 4 or 5 which correspond to having no problems, having slight problems, having moderate problems, having severe problems, and being unable to do/having extreme problem. As a result, a participants health state can be defined by a 5-digit number by combining the numeric levels from the 5 dimensions, ranging from 11111 (having no problems in all 5 dimensions) to 55555 (having extreme problem in all 5 dimensions). The US-based value set for the EQ-5D-5L will be derived using an international standardized protocol ([Pickard et al., 2019](#)).

The EQ-5D-5L will be completed by the participants at Day 1, Weeks 4, 8, 12, 16, 20, 24, 28, 32, 36, 40, 44, 48, 52, and 56.

#### **6.4.4. Repeated or Unscheduled Assessments of Safety Parameters**

Baseline is defined as the last assessment made before the first dose of study treatment. If end-of-study assessments are repeated or if unscheduled visits occur, the last non-missing postbaseline assessment will be used as the end-of-study assessment for generating summary statistics. However, all postbaseline assessments will be used for PCS value determinations, and all assessments will be presented in the data listings.

#### **6.4.5. Missing Date of the Last Dose of Study Treatment**

When the date of the last dose of the open-label study treatment is missing, all efforts should be made to obtain the date from the Investigator. If it is still missing after all efforts have been made, the last available study treatment date will be used in the calculation of treatment duration.

#### **6.4.6. Missing Severity Assessment for Adverse Events**

If severity is missing for an AE that started before the date of the first dose of open-label study treatment, a severity of mild will be assigned. If severity is missing for an AE that started on or after the date of the first dose of open-label study treatment, a severity of severe will be assigned. The imputed values for severity assessment will be used for the incidence summary; the values will be shown as missing in the data listings.

#### **6.4.7. Missing Causal Relationship to Study treatment for Adverse Events**

If the causal relationship to the open-label study treatment is missing for an AE that started on or after the date of the first dose of open-label study treatment, a causality of yes will be assigned. The imputed values for causal relationship to open-label treatment will be used for the incidence summary; the values will be shown as missing in the data listings.

#### **6.4.8. Missing Date Imputation**

The following imputation rules only apply to cases in which the start date for AEs is incomplete (i.e., partly missing).

##### **Missing month and day**

If the year of the incomplete start date is the same as the year of the first dose of open-label study treatment, the month and day of the first dose of open-label study treatment will be assigned to the missing fields.

If the year of the incomplete start date is before the year of the first dose of open-label study treatment, December 31 will be assigned to the missing fields.

If the year of the incomplete start date is after the year of the first dose of open-label study treatment, January 1 will be assigned to the missing fields.

##### **Missing month only**

If only the month is missing, the day will be treated as missing and both the month and the day will be replaced according to the above procedure.

##### **Missing day only**

If the month and year of the incomplete start date are the same as the month and year of the first dose of open-label study treatment, the day of the first dose of open-label study treatment will be assigned to the missing day.

If either the year of the incomplete start date is before the year of the date of the first dose of open-label study treatment or if both years are the same but the month of the incomplete start date is before the month of the date of the first dose of open-label study treatment, the last day of the month will be assigned to the missing day.

If either the year of the incomplete start date is after the year of the date of the first dose of open-label study treatment or if both years are the same but the month of the incomplete start date is after the month of the date of the first dose of open-label study treatment, the first day of the month will be assigned to the missing day.

If the stop date is complete and the imputed start date as above is after the stop date, the start date will be imputed by the stop date.

If the start date is completely missing and the stop date is complete, the following algorithm will be used to impute the start date:

- If the stop date is after the date of the first dose of open-label study treatment, the date of the first dose of open-label study treatment will be assigned to the missing start date
- If the stop date is before the date of the first dose of open-label study treatment, the stop date will be assigned to the missing start date

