## **2. Statistical Hypotheses**

Since the primary objective of this study is to assess the safety and tolerability over 52 weeks of atogepant 60 mg once daily treatment, there is no statistical hypothesis specified for the study.

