## 5. Statistical Analyses

### 5.1. General Considerations

- Efficacy endpoints will be analyzed descriptively based on the mITT population.
- Safety endpoints will be performed using the Safety population.
- Continuous variables will be summarized by number of participants with observed values (n), mean, standard deviation (SD), median, 1st and 3rd quartiles (Q1, Q3), minimum (min), and maximum (max).
- Categorical variables will be summarized by number of participants with observed values, events (n), frequency count (n1), and percentage of participants with observed values.
- Partial dates will be treated as missing in computation or in variable derivation unless specified otherwise, but will be listed in the data listings as they appear on the eCRF.
- For monthly endpoints, baseline is defined as assessments during the last 28 days of baseline period in the lead-in study for 3101-303-002 rollover participants, and the last 28 days of the screening/baseline period for De Novo EM Participants. For efficacy endpoints that are assessed at clinical visits, baseline is defined as the last non-missing efficacy assessment before the first dose of study intervention in the lead-in study (3101-303-002) for 3101-303-002 Completers, and the last non-missing efficacy assessment before the first dose of study for De Novo EM Participants. For each of the clinical, laboratory, vital sign, and ECG parameters, the baseline is defined as the baseline value in the lead-in study (3101-303-002) for 3101-303-002 Completers, and the last nonmissing safety assessment before the first dose of study drug for De Novo EM Participants.
- The change from baseline values will be computed as the post-baseline value minus the baseline value.
- Study intervention is treatment administered (atogepant 60 mg QD).
- All statistical analysis will be performed using SAS version 9.4 or higher.
- Medical Dictionary for Regulatory Activities (MedDRA), Version 27.0 or higher, will be used to code adverse events and medical history.
- WHO Drug Global B3 (v.202403 or higher) will be used to code medications.

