#### **5.4.3. Adverse Events**

Adverse events (AEs) will be coded using the Medical Dictionary for Regulatory Activities (MedDRA) version 27.0 or higher.

An AE will be considered as a treatment-emergent adverse event (TEAE) if the AE began or worsened (increased in severity or became serious) on or after the date of the first dose of open-label study treatment. An AE that occurs more than 30 days after the last dose of open-label study treatment or the safety follow-up visit (Visit 15) in this extension study whichever comes later will not be counted as a TEAE. Per case report form instructions, a new AE record will be created for any AE that worsens; therefore, TEAEs can be identified as those AEs captured in Study 3101-306-002 with recorded onset date on or after the date of the first dose of open-label study treatment and within 30 days after the last dose of open-label study treatment or Visit 15 whichever comes later.

An AE is a TESAE if it is a TEAE that additionally meets any SAE criterion below (as specified in the protocol Section 9.1.2):

- Results in death
- Is life threatening
- Requires inpatient hospitalization or prolongation of existing hospitalization
- Results in persistent disability/incapacity
- Is a congenital anomaly/birth defect
- Other situations that the medical or scientific judgment considers to be serious.

TEAEs that started after the date of last dose of open-label study treatment will be considered as newly emergent TEAEs (NEAEs).

TEAEs that started on or after the date of first dose of open-label study treatment will be summarized.

Overall summary of AEs will be provided on a per-participant basis for categories of TEAEs, treatment-related TEAEs, TESAEs, treatment-related TESAEs, TEAEs leading to study intervention discontinuation, and deaths.

The number and percentage of participants reporting TEAEs will be tabulated by system organ class (SOC) and preferred term (PT), and further categorized by severity. If more than 1 AE is coded to the same preferred term for the same participants, the participant will be counted only once for that preferred term using the greatest severity for the summarization by severity.

The number and percentage of participants reporting treatment-related TEAEs will be tabulated by SOC and PT.

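### SAP 6.4.8 uses an AE stop date only when it is complete, so an unresolved AE with unknown start gets no onset date and one narrow pre-treatment pattern is counted as treatment-emergent

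*SAP*

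**What the plan says.** SAP 6.4.8 opens by limiting its own scope: "The following imputation rules only apply to cases in which the start date for AEs is incomplete (i.e., partly missing"). It then gives these rules for AE start dates.

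- **Month and day unknown, year equal to the year of first dose:** "the month and day of the first dose of open-label study treatment will be assigned to the missing fields".
- **Check against the stop date:** the imputed start is replaced by the stop date under the condition "If the stop date is complete and the imputed start date as above is after the stop date".
- **Start completely missing:** "If the start date is completely missing and the stop date is complete, the following algorithm will be used to impute the start date". A stop after first dose gives an onset on the first-dose date. For the other direction, "If the stop date is before the date of the first dose of open-label study treatment, the stop date will be assigned" as the start. A stop on the first-dose date itself is not mentioned.

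No rule imputes a partial AE stop date, and the default in SAP 5.1 is "Partial dates will be treated as missing in computation or in variable derivation unless specified otherwise". SAP 5.4.3 gives the working test for treatment emergence: "TEAEs can be identified as those AEs captured in Study 3101-306-002 with recorded onset date on or after the date of the first dose". The dose meant is the open-label one, and the window runs to 30 days after last dose or Visit 15, whichever is later. A TESAE must first be a TEAE.

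The parallel rule for medications, SAP 6.4.9.1, makes the same check but accepts a stop date that is either complete or imputed.

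**The concern.** Safety is the primary objective, and the TEAE tables are its main output. Both uses of the AE stop date in 6.4.8 switch off when that date is incomplete, and this misdirects events in two ways.

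(a) Of two AEs with unknown onset, the one that resolved on treatment on a known date is counted, and the one that never resolved is given no onset. The unresolved event is the one a safety reviewer would least want to lose. The summaries affected are those by SOC and preferred term, severity, relatedness and discontinuation. The table of related TEAEs by onset interval cannot place an event without an onset at all.

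(b) A pre-treatment AE can be given an onset later than the month in which it is known to have ended, and so enter the TEAE tables.

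Where the plan has no rule, someone must decide case by case with open-label data in view.

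**Working it through.** The study has no hypothesis test (SAP 2: "there is no statistical hypothesis specified for the study"), and there is no stated figure to reproduce. The check applies the 6.4.8 rules and the 5.4.3 onset test literally to a set of start and stop patterns.

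**Inputs.** Rules: SAP 5.1, 5.4.3, 6.4.8 and 6.4.9.1. First dose: 15 Jun 2022. This is an assumed date; only its order relative to the AE dates matters. Cohort sizes: approximately 30 De Novo, at least 140 Completers and at least 170 overall (SAP 3). Common-TEAE cuts: 2% and 5% after rounding, in either cohort (SAP 5.4.3).

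| AE start | AE stop | Onset under 6.4.8 | TEAE? |
|---|---|---|---|
| Missing | Ongoing | None (no rule) | Not identified |
| Missing | Mar 2022, day unknown | None (no rule) | Not identified |
| Missing | Oct 2022, day unknown | None (no rule) | Not identified |
| Missing | 2023 only | None (no rule) | Not identified |
| Missing | 15 Jun 2022 (first-dose date) | None (no rule) | Not identified |
| Missing | 1 Oct 2022 | 15 Jun 2022 | Yes |
| Missing | 20 May 2022 | 20 May 2022 | No |
| 2022 only | 20 May 2022 | 20 May 2022 | No |
| 2022 only | May 2022, day unknown | 15 Jun 2022 | Yes |
| 2022 only | Ongoing | 15 Jun 2022 | Yes |
| May 2022 | May 2022, day unknown | 31 May 2022 | No |
| 2021 only | May 2022, day unknown | 31 Dec 2021 | No |

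**Reading for (a).** Rows 1 to 5 have no onset. Row 2 ended before first dose, so nothing is lost there. Rows 3 and 4 ended on treatment or later, yet fail the onset test only because part of the stop date is unknown. Row 6 differs from row 3 only in having a stop day, and it is counted. An ongoing AE whose start year is known (row 10) is also counted, so the gap is specific to a completely missing start.

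**Reading for (b).** Only row 9 is wrong: the imputed onset of 15 Jun falls after the known stop month of May. It requires a start known only to the year, that year being the year of first dose, a stop with unknown day, and a stop month before the first-dose month. Rows 7 and 8 show that a complete pre-dose stop gives the right answer. With the 6.4.9.1 wording, row 9 becomes 31 May 2022, not a TEAE. That wording does not change rows 1 to 5.

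**Size per affected participant.**

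- De Novo: 1/30 = 3.3%, above the 2% cut and below the 5% cut
- Completers: 1/140 = 0.7%
- Overall: 1/170 = 0.6%

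**The case against.** **Exclusion is not stated.** SAP 5.4.3 first defines a TEAE as an AE that began or worsened from first dose onward; the onset-date sentence is the operational version. The SAP never says that an AE without an onset is left out. This stands: exclusion under (a) is an inference from the working test, although it is the test a programmer would implement.

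**Such cases should be rare.** Protocol 6.1.1 requires start and stop dates for every AE, and participants are asked about AEs at visits four weeks apart. Pre-treatment AEs are collected only from consent, so (b) concerns mainly the De Novo screening window of Day -35 to Day -28 onward; Completers consent at Visit 1. This also stands. A contingency rule for missing starts is not evidence that the sponsor expects them.

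**Stronger readings that a reader might infer.**

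- *Serious events disappear.* They do not. SAP 4 lists SAEs and deaths for the Screened population, and SAP 5.4.3 adds separate displays for participants with SAEs and participants who died. ALT/AST, potential Hy's law and C-SSRS summaries come from laboratory and scale data, and discontinuation reasons also come from the disposition form.
- *Any AE that ended before treatment becomes a TEAE.* It does not; a complete pre-dose stop is handled correctly. Where (b) does occur, it adds an event and does not hide one.
- *The gap breaks a worst-case principle set in 6.4.6 and 6.4.7.* Those sections presuppose that the onset is already placed relative to first dose, and 6.4.6 assigns mild severity to AEs that began earlier. They set no principle for onset dates.

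**Conclusion.** The point holds as a narrow classification gap in the primary safety output. Followed as written, SAP 6.4.8 gives no onset to an AE with a completely missing start that is ongoing, partly dated at its stop, or stopped on the first-dose date. Under the 5.4.3 test such an AE is not identified as a TEAE or TESAE. In one specific pattern of year-only start and partial stop, 6.4.8 turns a pre-treatment AE into a TEAE.

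The number of affected AEs is not given and should be small. Even so, a single participant decides whether a preferred term clears the 2% cut in the De Novo cohort; the effect on the overall rate is about 0.6 percentage points. These sizes assume the planned cohort numbers and that the participant has no other qualifying event with that preferred term. The rules should be changed because the misclassification is clear and cheap to prevent, not because a large distortion has been shown.

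**What to change.** Amend SAP 6.4.8 in three places.

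1. **Completely missing start.** Assign the first open-label dose date unless the available stop information, complete or partial, shows that the AE ended before first dose. This covers ongoing AEs, partial stops that are not provably earlier, and a stop on the first-dose date. Where a complete stop date is earlier, keep the present rule and use the stop date.
2. **Partial stop date.** When its known year and month are before the month of first dose, cap the imputed start at the last day of that stop month. This brings the AE rule into line with 6.4.9.1. Borrowing the 6.4.9.1 wording alone is not enough: 6.4.8 has no AE stop-date imputation for it to refer to, and it would leave part (a) untouched.
3. **Scope sentence.** Extend it to completely missing starts. At present it limits the section to partly missing ones, while the section goes on to give a rule for the other case.

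In the table above, rows 1, 3, 4 and 5 would then take 15 Jun 2022 and be TEAEs. Row 2 would take 31 Mar 2022 and row 9 would take 31 May 2022; neither would be a TEAE. The other rows do not change.

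The cost is a few sentences and minor programming. The downside is that TEAE counts may rise slightly, because some AEs of unknown onset will be counted that in fact began before treatment.
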